The purpose of the WorkACTIVE-P study is to assess the outcome of an innovative multi-component intervention focused on increasing energy expenditure and re-balancing the disrupted energy balance equation of sedentary workplaces with an ultimate target of reducing workers' abdominal obesity. The energy expenditure intervention includes replacing workplace sedentary time with access to a dedicated pedal desk and increasing steps/day with wearable monitors. Both components are incorporated into an electronically-delivered behavior monitoring and support infrastructure, thus enabling continuous management. We will utilize pedal desks manufactured and owned by Pennington Biomedical Research Center to conduct this study at Blue Cross Blue Shield of Louisiana, Louisiana State University, Louisiana Office of Technology, Louisiana Healthcare Connections, and Pennington Biomedical Research Center offices in Baton Rouge, LA. 41 individuals will be recruited and randomized to either a control arm or combined Walk More Pedal Desk (WMPD) intervention. Primary (MRI-determined visceral adipose tissue) and secondary (changes in body weight, total adipose tissue, subcutaneous adipose tissue, blood pressure, blood lipids, fasting glucose and insulin, HbA1-c, free-living accelerometer-determined walking, time spent in sedentary behavior, exercise, and dietary intake) outcomes will be assessed at baseline and month 3.

II. Background and Significance

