Workstation Alternatives: Incipient reports support the feasibility of elevating net energy expenditure by replacing occupational sedentary behavior with low-intensity non-exercise physical activity via “workstation alternatives” to the traditional seated computer-and-desk-based combinations. For example, Edelson and Danoff²³ introduced the feasibility of performing computer-based work while walking on a treadmill in 1989, and Levine and Miller popularized the concept with a publication in 2007 demonstrating its ability to elevate energy expenditure over the seated condition.⁸ [name] recently published a systematic review⁵ reporting the comparative potential for workstation alternatives (including stability balls, sit-to-stand desks, treadmill desks, and pedal desks) to elevate occupational energy expenditure. Active workstations (i.e., specifically treadmill desks and pedal desks) offer the greatest promise (approximately 2-4 kcal/min compared to 1.2 kcal/min in the traditional seated working condition), but only to the extent that workers find them acceptable, tolerable, and congruent with their primary working tasks and therefore frequently use them for extended periods of time. [name] has recently completed a randomized controlled trial implementing treadmill desks in a real world workplace and have documented a number of challenges to widespread adoption and thus scalability of treadmill desks (recently published¹¹). In response to these challenges, we have developed a much more affordable, convenient, integrated and tolerable pedal desk: a semi-recumbent (upright) portable pedal station with a maneuverable and adaptable desktop. Workers are able to complete their tasks comfortably in a more traditional seated position. The cost and size of the device makes it feasible for workers to have their own dedicated pedal desk rather than sharing access (as we have learned, a scheduling and management impediment) to larger and more expensive treadmill workstations.¹¹ Alternative pedal device designs (notably those that slide under conventional desks) have not yet facilitated extended use in workers,⁷ in part because workers “bang their knees” against the desk. [name] pilot data collection in 10 workers to date indicate that pedal desk use can more than double the energy expenditure of seated computer based work.

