Increasing Steps/day with Wearable Step Counters: Steps/day is an increasingly utilized metric for objectively capturing and representing total daily walking.^{24,25} Researchers recently reported 5-year changes in body mass index (BMI), waist-to-hip-ratio, and insulin sensitivity related to 1,000 step incremental changes in step-defined physical activity.²⁶ Meta-analyses indicate that step-counting interventions can expect to realize incremental increases in walking behavior on the order of 2,000-2,500 steps/day. The Co-Investigator of this R21 is a world leader in such interventions.^{25,27,28} She developed a self-selected goal approach that elicited up to an extra 4,000 steps/day in individuals with Type 2 diabetes,² and was subsequently adapted and delivered as a workplace intervention that elicited a 3,500 steps/day change.¹ As reported in a recent meta-analysis,²⁹ at least four other controlled workplace studies have incorporated wearable step-counters into multi-component interventions. The inclusion of a pedal desk is novel. No one has previously estimated the relative contributions of independent intervention components to changes in abdominal obesity.

A Combined Approach: Pedaling actions are largely ignored by waist-worn step counters.³⁰ Therefore, layering a step-counting intervention on top of a pedal desk intervention permits a clear evaluation of their separate and combined dose-response effects. Daily electronic tracking of pedal desk use (duration, rpm, estimated distance and energy expenditure) and steps/day via automatic internet-based software enables continuous tracking of both behaviors for tailored feedback, behavioral shaping, and evaluation purposes. **WorkACTIVE-P** will clearly inform the feasibility of combining these distinct yet compatible components of a workplace multi-component energy expenditure intervention.

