In response to these challenges, researchers have begun to consider⁷ how modern occupational practices and environments could be enriched to facilitate, rather than discourage, increased energy expenditure by replacing sedentary behaviors with opportunities for non-exercise physical activity without competing with time committed to work tasks. For example, in 2007 Levine and Miller described a "walk-and-work desk," a treadmill and desk combination.⁸ Since that time, Thompson et al.⁹ reported a positive treadmill desk feasibility study with nurses, clinical assistants, and secretaries and John et al.¹⁰ published the pre-post impact of a 9-month treadmill desk intervention in 12 sedentary office workers. Between baseline and 9 months, median steps/day increased from 4352 to 7080 and average waist circumference decreased 5.5 cm. Despite these initial positive reports, [name] pilot randomized controlled study of treadmill desks in a local workplace (recently published¹¹) suggest that there are many behavioral and logistical challenges, including financial (treadmills desks are \$4000-6000) challenges, that make widespread adoption formidable. In direct response to these identified challenges, we have fashioned a much more affordable (approximately \$800), convenient, integrated and user-friendly pedal desk: a semi-recumbent (upright) pedal station with an attached, maneuverable and adaptable desktop capable of supporting a large computer monitor. Workers are able to complete their tasks comfortably in a more traditional seated position. The cost and size of the device makes it feasible for workers to have their own dedicated pedal desk rather than sharing access to larger and more expensive treadmill workstations. We believe that the combination of using a pedal desk while also increasing steps/day will provide workers with flexible and compatible strategies for effectively combating the low energy expenditure of a sedentary working lifestyle.

b. Primary Aims and Hypotheses:

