- **Accelerometry (Physical Activity):** Participants will be instructed to wear the GT3X+ accelerometer (ActiGraph, LLC, Pensacola, Florida, USA) at their waist for seven consecutive days, approximately 24 hrs/day. We have successfully used this 24-hour protocol in diverse populations including children, adults, and older adults and find it maximizes wear time. This accelerometer has been validated^{35,36} and is one of the most widely used accelerometers in research and has the capability of detecting minute-by-minute physical activity intensity and sedentary behavior using previously validated activity count cut points.^{36,37} Participants enrolled in the WMPD Intervention Group will be fitted with a FitBit® activity monitor to wear at their waist during the intervention. Participants will be asked to wear the FitBit® for all 12 weeks of the intervention, removing it only for activities involving water, such as baths or swimming, and while sleeping.
- **Blood Draws:** Participants will be asked to fast at least 12 hours prior to blood draw. In addition, participants will be asked to refrain from consuming alcohol or participating in an exercise training session at least 24 hours prior to blood withdrawal. Fasting levels of glucose, insulin, HOMA-IR, HbA1c, and blood lipids will be analyzed. Approximately 12 mL of blood will be collected at SV1 and Month 3 visits, which is a total of 24 mL during the course of the study.
- **Blood pressure:** Blood pressure will be measured at rest. Two measures will be taken with a heart rate in between. The average will be recorded per standard Pennington Biomedical's procedures.

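### Accelerometer sedentary time makes no allowance for seated pedalling, so this secondary outcome may understate the WMPD-control difference; the pedal log can bracket it

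*Combined protocol and SAP*

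**What the plan says.** All references are to the combined protocol and SAP.

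- **Outcome.** Time in sedentary behaviour is listed as a secondary outcome in the opening purpose statement, section II.b (Additional Aims) and section III.
- **Measurement.** Section VI.a (Accelerometry) has participants "wear the GT3X+ accelerometer (ActiGraph, LLC, Pensacola, Florida, USA) at their waist for seven consecutive days, approximately 24 hrs/day". It describes the device as able to detect "minute-by-minute physical activity intensity and sedentary behavior using previously validated activity count cut points". Section VI requires at least 4 days with at least 10 hours of wear at baseline. No other non-wear rule is given.
- **Status of pedalling.** The purpose statement says: "The energy expenditure intervention includes replacing workplace sedentary time with access to a dedicated pedal desk". Item 6 of the Innovation list in section II likewise treats pedal-desk use as low-intensity activity that replaces sedentary work. Pilot data in section II (Workstation Alternatives) indicate that "pedal desk use can more than double the energy expenditure of seated computer based work".
- **Posture.** Section II.a says: "Workers are able to complete their tasks comfortably in a more traditional seated position".
- **Detection.** Section II (A Combined Approach) says: "Pedaling actions are largely ignored by waist-worn step counters". It presents this as an advantage, because layering the two components "permits a clear evaluation of their separate and combined dose-response effects".
- **Pedal log.** The same paragraph says electronic tracking enables "continuous tracking of both behaviors for tailored feedback, behavioral shaping, and evaluation purposes". Section VII.b uses the log for adherence and section IX.d for weekly summaries. The regression of VAT change on the two components (section II.b) may also draw on it. Nothing links the log to sedentary time.

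**The concern.** The plan does not regard pedalling as sedentary, yet measures sedentary time with a waist-worn device and a count rule that has no provision for it. The section that explains why waist-worn step counters miss pedalling does not consider what a similar blind spot would do to this outcome.

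Any such error would be differential. Controls keep their usual work (section VII.a), so desk pedalling occurs in one arm only and after baseline only. The month-3 accelerometer is issued a week before a visit about 3 months after the intervention starts (section VI), so the wear week falls near the end of a 12-week intervention, when desk use is presumably at its working level. Each pedalling minute scored as sedentary takes one minute off the between-arm difference.

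Replacing sedentary time is the desk's stated mechanism, and the pilot is meant to lead to a full-scale trial. A small or null result could be read as the desk failing to do this when the device had simply not seen it. Deciding how to credit pedalling after seeing the data would be post hoc.

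**Working it through.** **The plan's own figures.** The plan gives no expected change, SD or power for sedentary time. Its one sample-size figure concerns VAT and reproduces: 2 × (1.96 + 0.84)² × (1.20/1.15)² = 17.1, so 18 per arm, and 18/0.90 = 20 with attrition. Power at 18 per arm is 0.82 (normal) or 0.80 (t). Nothing below touches it.

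**Inputs**
- *h*, pedal hours per workday: 2 to 4, from the example goals in section VII.b, where pilot workers also estimated a median of 4 h.
- 5 workdays in the 7-day wear week: assumption.
- *d*, the fraction of pedalling the GT3X+ rule already scores as non-sedentary: not in the documents, so 0, 0.5 and 1 are shown.
- Added walking: 30 min/day (210 min/week). This is 3,000 extra steps (section II.b) at 100 steps/min, a rate assumed from a reference title in section X (3,000 steps in 30 minutes).
- Pedalling and walking displace sitting minute for minute: assumption.
- Controls do no desk pedalling.

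**Step 1: understatement.** Minutes/day missed = 60 × 5 × h × (1 − d)/7 = 300h(1 − d)/7.

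| | d = 0 | d = 0.5 | d = 1 |
|---|---|---|---|
| h = 2 | 600/7 = 86 | 300/7 = 43 | 0 |
| h = 4 | 1200/7 = 171 | 600/7 = 86 | 0 |

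**Step 2: recorded share of the true reduction** = (210 + 300hd)/(210 + 300h).

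| | d = 0 | d = 0.5 | d = 1 |
|---|---|---|---|
| h = 2 | 210/810 = 26% | 510/810 = 63% | 100% |
| h = 4 | 210/1410 = 15% | 810/1410 = 57% | 100% |

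The recorded reduction is not zero even at d = 0, because added walking is still counted.

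**Step 3: other inputs.**
- 75% of the goals, h = 1.5 to 3 (this applies the session threshold of section VII.c to time, an assumption): 210/660 = 32% to 210/1110 = 19% at d = 0, and 435/660 = 66% to 660/1110 = 59% at d = 0.5.
- h = 1 (assumed): 210/510 = 41% and 360/510 = 71%.
- Walking of 50 min/day (about 5,000 steps, the pilot increase in section VII.b), h = 2 to 4: 350/950 = 37% to 350/1550 = 23% at d = 0, and 650/950 = 68% to 950/1550 = 61% at d = 0.5.

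**Step 4: subtracting all logged minutes.** Share of the true reduction = (210 + 300hd + 300h)/(210 + 300h).

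| | d = 0 | d = 0.5 | d = 1 |
|---|---|---|---|
| h = 2 | 100% | 1110/810 = 137% | 1410/810 = 174% |
| h = 4 | 100% | 2010/1410 = 143% | 2610/1410 = 185% |

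For any d from 0 to 1, the unmodified version is at or below the true reduction and the full-credit version at or above it. The width of the bracket is the logged pedalling itself, 300h/7 = 86 to 171 min/day.

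**Step 5: non-wear.** If undetected pedalling were removed as non-wear, the min/day reduction would not be attenuated by it, but WMPD wear time would fall by up to 86-171 min/day. The truth then sits at the unmodified end of the bracket.

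**The case against.** Five points can be made for the plan.

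1. *The key link is undocumented.* The remark in section II concerns step counters, and activity counts are a different signal. The documents do not report how the GT3X+ responds to pedalling. Section VIII.a even describes accelerometers as worn on the arm, which conflicts with the waist placement in section VI.a and needs reconciling. This stands: a reader might infer that the device will miss pedalling, but the documents support only the possibility.
2. *A scoring rule exists.* A reader might infer that sedentary time has no rule at all. Read as a rule, section VI.a classifies each minute by counts, identically in both arms. This stands too: what is missing is any provision for pedalling.
3. *The range is wide and its inputs are goals.* A span of 0 to 171 min/day shows no likely size, and section VII.c itself expects some shortfall in desk use. That is fair, and it is why a bracket is more useful than a point correction.
4. *The pedal-minute summary already guards against misreading.* It would show that the desk was used, so the risk is reduced. It would not show how much of that use the sedentary-time estimate already includes.
5. *Under a posture-only definition nothing is understated.* True, but the plan states no such definition, and its premise that pedalling replaces sedentary time points the other way.

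The 24-hour wear protocol also gives no rule separating sleep from sedentary time. That gap concerns both arms and is distinct from this point.

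**Conclusion.** The point holds in conditional form. The default scoring makes no allowance for seated pedalling. To the extent that GT3X+ counts miss it, the WMPD-control difference in sedentary time is biased toward the null, by 0 to 86-171 min/day at 2 to 4 h on 5 workdays. With 30 min/day of added walking, 15-26% of the true reduction would be recorded if no pedalling were detected, 57-63% if half were, and 100% if all were. These figures assume that the goals are met, that both activities displace sitting, that undetected pedalling is scored as sedentary, and that the desk is still in use in the month-3 wear week.

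Two stronger readings are not supported. One is that the sedentary-time result will be null or uninterpretable: walking is still recorded and the detection fraction is unknown. The other is that the trial's main conclusion is at risk: VAT is measured by MRI, and neither it nor its power depends on the accelerometer. This is one secondary outcome in a pilot, and the change is a cheap improvement that alters what can be concluded from it.

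**What to change.** In sections VI.a and IX.d:

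- State whether pedalling counts as sedentary.
- Keep unmodified accelerometer sedentary time as the planned outcome, labelled as not credited for pedalling. Say that a small difference on it alone will not be taken to mean that the desk failed to reduce sedentary time.
- Pre-specify a month-3 sensitivity analysis that subtracts the logged pedalling minutes for the wear days. Report the two versions together as no credit and full credit.
- If the log stores time stamps, instead reclassify as non-sedentary only worn epochs scored sedentary that overlap logged pedalling.
- State one non-wear rule, apply it identically in both arms, and report wear time by arm.
- Note that accelerometer steps and moderate-to-vigorous time may also not capture pedalling.

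**Cost.** Some SAP wording and a data link for about 20 WMPD participants, with no new devices or visits. The epoch version needs aligned clocks and minute-level time stamps, which the documents do not show to exist.

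**Downside.** The log exists only in WMPD, so the adjustment can only lower sedentary time in that arm. Full subtraction may double-count pedalling already detected, by up to 86-171 min/day at the example goals, and may credit time when the device was not worn. It is therefore a bound and not a replacement for the planned outcome.
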